Recording of MAEs (Section 8.3)		●	●	●	●	●	●
Recording of SAEs (Section 8.3)		●	●	●	●	●	●
Recording of SAEs related to study participation or to a concurrent GSK medication/vaccine (Section 8.3)	●	●	●	●	●	●	●
Recording of pIMDs (Section 8.3)		●	●	●	●	●	●
Recording of AEs leading to withdrawal from the study intervention or withdrawal from study (Section 7)		●	●	●	●	●	●
Recording of pregnancies and pregnancy outcome (Section 8.3)		●	●	●	●	●	●
Study conclusion (Section 4.4)							●

AE: adverse event; CMI: cell-mediated immunity; CCI: cell-mediated immunity; MAE: medically attended event; PBMC: peripheral blood mononuclear cell; pIMD: potential immune-mediated disease; SAE: serious adverse event.

Note: The double-line borders indicate the analyses which will be performed on all data obtained up to these timepoints (refer to Section 9.3.5).

● is used to indicate a study procedure that requires documentation in the individual electronic Case Report Form (eCRF).

○ is used to indicate a study procedure that does not require documentation in the individual eCRF.

* Screening evaluations may be completed up to 56 days before Visit 1 (Day 1). Study staff should allow sufficient time between the Screening visit and Visit 1 to receive and review HSV testing results, and hematology/biochemical results. If deemed necessary by the investigator, re-testing can be performed within the allowed interval. Only data from the re-sampling testing, if done, will be taken into consideration.

** Blood sampling and pregnancy test to be performed before each study intervention administration.

CONFIDENTIAL218459 (TH HSV REC-004)
Protocol Final

*** The preferred location for measuring temperature will be the oral cavity. Study intervention administration should not occur in case of fever (defined as temperature $\geq 38.0^{\circ}\text{C}$, regardless of the location of measurement).

Optional blood sampling. A separate informed consent form (ICF) will be signed by participants who agree to give their blood sample for this optional blood sampling.

Table 2 **Intervals Between Study Visits**

Interval	Reference Visits	Planned Visit Interval	Allowed Interval Range
Screening (Day -56) → Visit 1 (Day 1)	Screening visit		Up to 56 days*
Visit 1 (Day 1) → Visit 2 (Day 8)	Study intervention administration Dose 1	7 days	7 – 9 days
Visit 1 (Day 1) → Visit 3 (Day 29)		28 days	28 – 33 days**
Visit 3 (Day 29) → Visit 4 (Day 36)	Study intervention administration Dose 2	7 days	7 – 9 days

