3. OBJECTIVES, ENDPOINTS, AND ESTIMANDS

Table 3 Study objectives, endpoints and estimands

Objectives	Endpoints and estimands
Primary	
To evaluate the reactogenicity and safety of the HSVTI.	
 Percentage of participants reporting each solicited administration site event (redness, pain, and swelling) within 7 days (Day 1-Day 7) post-each dose. Percentage of participants reporting each solicited systemic event (fever, fatigue, headache, myalgia, arthralgia) within 7 days (Day 1-Day 7) post-each dose. Percentage of participants reporting unsolicited AEs within 28 days (Day 1-Day 28) post-each dose. Percentage of participants reporting MAEs from Dose 1 (Day 1) up to 28 days post-Dose 2 (Day 57). Percentage of participants reporting SAEs from Dose 1 (Day 1) up to 28 days post-Dose 2 (Day 57). Percentage of participants reporting newly diagnosed pIMDs from Dose 1 (Day 1) up to 28 days post-Dose 2 (Day 57). Percentage of participants reporting exacerbation of pre-existing pIMDs from Dose 1 (Day 1) up to 28 days post-Dose 2 (Day 57). Percentage of participants reporting any hematological and biochemical laboratory abnormalities at pre-study intervention administration (Day 1), post-Dose 1 (Day 8 and Day 29), and post-Dose 2 (Day 36 and Day 57).
Secondary	
To evaluate the humoral immune response induced by the HSVTI.	
 CCI antibody GMC and seropositivity rate (assessed by ELISA) at pre-study intervention administration (Day 1), 28 days post-Dose 1 (Day 29), and 28 days post-Dose 2 (Day 57).
To evaluate the cellular immune response induced by the HSVTI.	
 Geometric mean of CCI CD4+/CD8+ T-cells frequency expressing at least 2 activation markers (IFN-γ, TNF-α, IL-2, IL-13, IL-17, 4-1BB and/or CD40L) and including at least one cytokine (assessed by CFC) at pre-study intervention administration (Day 1), 28 days post-Dose 1 (Day 29) and 28 days post-Dose 2 (Day 57).
To evaluate the safety of the HSVTI up to the end of follow-up period.	
 Percentage of participants reporting MAEs from Dose 1 (Day 1) up to study end (Day 209). Percentage of participants reporting SAEs from Dose 1 (Day 1) up to study end (Day 209). Percentage of participants reporting newly diagnosed pIMDs from Dose 1 (Day 1) up to study end (Day 209). Percentage of participants reporting pre-existing pIMDs from Dose 1 (Day 1) up to study end (Day 209).

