7.1.1. Contraindications to subsequent study intervention(s) administration

The eligibility for subsequent study intervention administration must be confirmed before administering any additional dose.

Participants who meet any of the criteria listed below should not receive additional doses of study intervention. Such participants should be encouraged to continue other study procedures, at the investigator's discretion (Section 10.3.9.2). All relevant criteria for discontinuation of study intervention administration must be recorded in the eCRF.

- Participants who experience any SAE judged to be related to study intervention or non-study concomitant vaccine/product.
- Participants who develop any new condition which, in the opinion of the investigator, may pose additional risk to the participants if they continue to participate in the study.
- Occurrence of a new pIMD or the exacerbation of an existing pIMD that, in the opinion of the investigator, expose the participant to unacceptable risk from subsequent vaccination. In such cases, the investigator should use his/her clinical judgment prior to administering the next dose of study intervention. Refer to Section 10.3.6.1 for the definition of pIMDs.
- Abnormal hematological and biochemical parameters, unless the laboratory abnormalities are considered temporary or not clinically significant by the investigator.
- Occurrence of an AE assessed as related to the study intervention following the previous dose administration, which may place the participant at unreasonable or significant risk of injury or illness following repeat exposure to study intervention, based on the investigator's judgment.
- Anaphylaxis or other hypersensitivity reactions following the administration of study intervention.
- Any condition that in the judgment of the investigator would make intramuscular injection unsafe.
- Pregnant or lactating.

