8.2.3.1. Study Holding Rules

Holding rules to be applied during the Study Intervention Administration Phase are presented in [Table 10](#). Meeting any of these holding rules will trigger a hold of study intervention irrespective of number of participants enrolled and/or timing of the event.

- Holding rules 1a-1d will be monitored by the investigators on a continuous basis throughout the study. Meeting any of these holding rules will trigger a hold of study intervention administration, irrespective of number of participants enrolled and/or timing of the event.

If an investigator detects one of the holding rules mentioned above, the study intervention administration will be immediately put on hold. GSK will be immediately informed and the data will be entered in the eCRF. It is GSK's responsibility to put the study intervention administration on hold at all sites.

- Holding rules will be assessed by the iSRC during safety evaluations on unblinded data. Meeting any of these holding rules will trigger a hold of study intervention administration.

Of note, no formal holding rules will be applied for other safety data such as non-life-threatening SAEs (those that are not meeting the definition of holding rule 1b), missed visits due to study intervention related AEs, Grade 1 and Grade 2 solicited and unsolicited AEs in the 7-day follow-up period and unsolicited AEs collected from 7 to 28 days after study intervention administration (refer to [Section 10.3.10.1](#) for assessment of intensity). However, to the extent of their availability, these data will also be reviewed by the SRT and iSRC to allow an overall assessment of the benefit/risk ratio of study intervention administration.

Table 10 Study Holding Rules

[figure not shown]
Holding Rule	Event	Number of Participants
1a	Death or any life-threatening SAE , regardless of causality	≥ 1
1b	Any non-life-threatening SAE that can be reasonably attributed to the study intervention administration	≥ 1
1c	Any withdrawal from the study (by investigator's or participant's request) and/or study intervention administration, following a Grade 3 AE	≥ 1
1d	Any solicited administration site or solicited systemic AE leading to hospitalization , or necrosis at the injection site, with an event onset within the 7-day (Days 1-7) post-study intervention administration period	≥ 1

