2a	Any Grade 3 solicited administration site AE (lasting 48 hours or more) in an investigational group, with an event onset within the 7-day (Days 1-7) post-study intervention administration period	≥ 25% (and ≥ 2 participants in each HSVTI group)
2b	Any Grade 3 solicited systemic AE (lasting 48 hours or more) in an investigational group, with an event onset within the 7-day (Days 1-7) post-study intervention administration period	≥ 25% (and ≥ 2 participants in each HSVTI group)
2c	Any Grade 3 unsolicited AE in an investigational group, that can be reasonably attributed to the study intervention administration, with an event onset within the 28-days (Days 1-28) post-study intervention administration period OR Any Grade 3 abnormality* in pre-specified hematological or biochemical laboratory parameters in an investigational group, between Day 1 and Day 29 post-study intervention administration period	≥ 25% (and ≥ 2 participants in each HSVTI group)

AE: adverse event; **SAE:** serious adverse event

*Grading of laboratory parameters will be based on the FDA Guidance for Industry "Toxicity Grading Scale for Healthy Adult and Adolescent Volunteers Enrolled in Preventive Vaccine Clinical Trials" (see [Table 18](#)).

[Figure 2](#) illustrates the probability to reach the study holding rules following study intervention administration:

- For holding rules 1, using a cut-off of 1/20, there is more than 80% chance that the holding rule is met for a study intervention with a true incidence rate above 8% and there is more than 36% chance that the holding rule is not met for a study intervention with a true incidence rate below 5%.
- For holding rules 2, using a cut-off of 5/20, there is more than 80% chance that the holding rule is met for a study intervention with a true incidence rate above 32% and there is more than 63% chance that the holding rule is not met for a study intervention with a true incidence rate below 20%.

Figure 2 Risk Assessment Curves for Study Holding Rules

If a holding rule is met, the investigator must suspend administration of the study intervention and inform GSK immediately (e.g. holding rules 1a-d). Refer to [Table 13](#) for contact information. GSK will inform the investigator if holding rules 2a-c are met.

The following communication sequence must be followed:

- The concerned study staff must put study interventions administration on hold.

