10.3.7. Clinical laboratory parameters and other abnormal assessments qualifying as AEs or SAEs

In the absence of a diagnosis, abnormal laboratory findings assessments or other abnormal results the investigator considers clinically significant will be recorded as an AE or SAE, if they meet the definition of an AE or SAE (refer to Sections [10.3.1](#) and [10.3.2](#)).

The investigator(s) must exercise their medical and scientific judgment in deciding whether an abnormal laboratory finding, or other abnormal assessment is clinically significant.

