10.3.9.1. Time period for collecting and recording AEs, SAEs, pIMDs and pregnancies

All AEs that occur during 7 days following administration of each dose of study intervention (Day 1 to Day 7) must be recorded into the appropriate section of the eCRF, irrespective of their intensity or whether or not they are considered related to the study intervention.

All unsolicited AEs that occur during 28 days following administration of each dose of study intervention (i.e., on the day of study intervention administration and 27 subsequent days) must be recorded into the appropriate section of the eCRF, irrespective of their intensity or whether or not they are considered related to the study intervention.

The time period for collecting and recording SAEs (all, fatal and related) will begin at the first receipt of study intervention (Day 1) and will end at study end (Day 209). See Section 10.3.11 for instructions on reporting of SAEs. However, any SAEs assessed as related to study participation (e.g., Protocol-mandated procedures, invasive tests or change in existing therapy) or related to a GSK product will be recorded from the time a participant consents to take part in the study (i.e., at the Screening visit).

All AEs/SAEs leading to withdrawal from the study will be collected and recorded from the time of the first receipt of study intervention (Day 1) until study end (Day 209).

The time period for collecting and recording MAEs will begin at the first receipt of study intervention (Day 1) and will end at study end (Day 209).

The time period for collecting and recording pIMDs will begin at the first receipt of study intervention (Day 1) and will end at study end (Day 209). See Section 10.3.11 for instructions on reporting of pIMDs.

The time period for collecting and recording pregnancies will begin at the first receipt of study intervention (Day 1) and will end at study end (Day 209). See Section 10.3.11 for instructions on reporting of pregnancies.

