#### **6.2.3.5. Onset day**

The onset day for an event (e.g. AE, concomitant medication/vaccination) is the number of days between the last (i.e., most recently received) study dose (i.e., it may be dose 1 or dose 2 of the study intervention) and the start date of the event plus one day. This is 1 for an event occurring on the same day as a study dose (and reported as starting after study dose) and e.g., 2 for an event occurring on the day after the study dose was given.

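### Rule 2c's laboratory window ends at post-dose Day 29, but Table 2 permits Visit 5 up to post-dose Day 34, so a Grade 3 value at a compliant late Visit 5 falls outside it; for a late Visit 3 the rule is silent

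*Protocol*

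**What the plan says.** Table 10 in Protocol Section 8.2.3.1 gives rule 2c two limbs. The adverse event limb takes related Grade 3 unsolicited events with onset on Days 1 to 28 after a dose. The laboratory limb takes Grade 3 abnormalities "in an investigational group, between Day 1 and Day 29 post-study intervention administration period", with no causality condition. Either limb triggers a hold at 25% of an investigational group, subject to a minimum of two participants.

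Table 2 in Section 1.3 plans Visit 3 at 28 days after Dose 1 and Visit 5 at 28 days after Dose 2, and permits 28 to 33 days for each. Hematology and biochemistry are sampled at both visits. At Visit 3 the sample precedes Dose 2: "Blood sampling and pregnancy test to be performed before each study intervention administration".

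Both documents count the dosing day as Day 1. Protocol Section 10.3.9.1 describes the 28-day collection period as "on the day of study intervention administration and 27 subsequent days". SAP Section 6.2.3.5 says of the onset day: "This is 1 for an event occurring on the same day as a study dose".

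**The concern.** The laboratory limb runs one day longer than the adverse event limb in the same cell. The likely reason is to take in the planned 28-day sample. It does so with no tolerance, although Table 2 allows that visit five further days.

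Rule 2c is the only holding rule with a group-level laboratory trigger, and meeting it makes a hold mandatory. On a literal count, whether a compliant sample contributes depends on which permitted day the participant attends. If late values arise, the iSRC would have to choose a reading of its own rule after seeing unblinded data. Near the threshold a single participant decides the outcome.

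**Working it through.** **The plan's own figure.** Section 8.2.3.1 states that, with a cut-off of 5/20, rules 2 are met with more than 80% chance above a true rate of 32%, and not met with more than 63% chance below 20%. With X binomial (20, p):

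- P(X ≥ 5) at p = 0.32 is 0.817.
- P(X ≤ 4) at p = 0.20 is 0.630 (0.6296 at exactly 20%, a rounding matter).

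Both figures reproduce. They presume that every qualifying event is counted.

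**Dates.** Post-dose day = days elapsed since the dose + 1.

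| Sample | Permitted interval (Table 2) | Post-dose days | Inside Days 1–29? |
|---|---|---|---|
| Visits 2 and 4 | 7–9 days | 8–10 | Always |
| Visits 3 and 5, planned | 28 days | 29 | Yes |
| Visits 3 and 5, permitted | 28–33 days | 29–34 | Day 29 only |

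From the visit labels, planned Visit 3 is 29 − 1 + 1 = Day 29 after Dose 1, and planned Visit 5 is 57 − 29 + 1 = Day 29 after Dose 2. Days 30 to 34 are outside, which is 5 of 6 permitted days. If the limit meant 29 elapsed days, 30 to 33 elapsed days would still be outside, which is 4 of 6.

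**Visit 5.** No later dose period can take in the sample. The adverse event limb has closed at Day 28. No dose remains to be withheld, so rule 1c could apply only through withdrawal from the study after a Grade 3 event. A value on Days 30 to 34 is therefore outside rule 2c on the stated day count.

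**Visit 3.** The sample is drawn before Dose 2. Two readings are open:

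- It belongs to Dose 1 and falls on Days 30 to 34, outside the window. In support, the primary laboratory endpoint in Section 3 lists its timepoints as "post-Dose 1 (Day 8 and Day 29), and post-Dose 2 (Day 36 and Day 57"), and SAP Section 6.2.1 assigns a same-day pre-dose event to the earlier dose. That SAP rule is written for events, so it is supportive only.
- If Dose 2 is given that day, the sample shares a calendar day with Day 1 of the Dose 2 period and counts there.

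Rule 2c does not choose between them. Where the abnormality is recorded as a Grade 3 adverse event and Dose 2 is withheld because of it, the question falls away. Rule 1c covers withdrawal from the study "and/or study intervention administration, following a Grade 3 AE", at one participant and with no time window. The open cases are those where rule 1c does not apply. Section 7.1.1 bars Dose 2 for "Abnormal hematological and biochemical parameters, unless the laboratory abnormalities are considered temporary or not clinically significant by the investigator", so a value judged temporary need not stop dosing. Under Section 10.3.7 only "abnormal results the investigator considers clinically significant will be recorded as an AE or SAE", so a laboratory Grade 3 is not automatically a Grade 3 adverse event.

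**Effect at the threshold.** Take a group of 20 with the two-participant minimum satisfied. Then 5/20 = 25% meets the rule and 4/20 = 20% does not, so one uncounted participant can change the result.

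**Illustration only.** Let f be the share of affected participants whose only Grade 3 value is uncounted because it falls on Days 30 to 34. The documents give no value for f, so it is an assumption. The counted rate is 0.32 × (1 − f).

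| f | Counted rate | P(X ≥ 5), n = 20 |
|---|---|---|
| 0 | 0.320 | 0.817 |
| 0.10 | 0.288 | 0.725 |
| 0.25 | 0.240 | 0.544 |
| 0.50 | 0.160 | 0.206 |

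The table shows direction. It does not estimate the loss.

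**The case against.** The best defence is that Day 29 is nominal. Scheduled laboratory samples exist only at visits, and the protocol labels visits by planned day while allowing a range. The primary laboratory endpoint names days with no range, and nobody would read it as dropping compliant late samples. The Day 1 conventions cited above concern adverse event collection and onset, not sampling. If rule 2c means the planned 28-day visit, nothing is lost. This argument has weight as to intent. It does not settle the text: Day 29 is the label of Visit 3 only, Visit 5 is labelled Day 57, and so for Dose 2 the limit has to be a post-dose count. No readable passage says that a late sample is treated as falling on the planned day. Section 8.2.3.1 says that a hold applies whatever the timing of the event, but this describes the consequence once a rule is met and does not widen a rule's own window.

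The second defence is that other safeguards cover the gap. Under Sections 8.2.3 and 8.2.3.2 the iSRC reviews all accumulated unblinded safety data about monthly, and a safety concern leads to the same immediate hold as a met rule. That largely stands. What is missing is the automatic trigger, because recognising a concern is a matter of judgement.

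A reader might infer that every late Visit 3 value is lost as well. The documents do not support this, because the sample may count on Day 1 of the Dose 2 period or be caught by rule 1c. A reader might also take 5 of 6 as the share of samples lost. It counts permitted calendar days; the planned day is inside the window.

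**Conclusion.** The mismatch is real and minor. It is firm for Visit 5: on the stated day count, a Grade 3 laboratory value at a compliant visit on post-dose Days 30 to 34 does not count toward the 25% trigger. For a late Visit 3 pre-dose sample the finding is only that the rule is silent, outside the cases where rule 1c already applies.

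The lost protection cannot be quantified from the documents. With no late visits it is zero. Any hold based on Visit 5 data could protect only participants still awaiting a dose. The conclusion assumes that the dosing-day convention applies to rule 2c and that the iSRC charter, which SAP Section 1 mentions but which is not available here, does not already define the window by visit. The documents do not support a claim that safety oversight fails.

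**What to change.** In Table 10, keep the laboratory window of rule 2c and extend it: Day 1 to Day 29 after a dose or, if later, up to and including the sample from the 28-day post-dose visit. Name that sample as the Visit 3 pre-dose sample for Dose 1 and the Visit 5 sample for Dose 2. State that the Visit 1 pre-dose sample is baseline and does not count. The threshold stays as it is.

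The day count should be extended, not replaced by a list of scheduled samples. Section 8.3.2.1 calls for clinically significant values to be repeated, and unscheduled or out-of-interval samples within Days 1 to 29 count today. A list restricted to scheduled samples within their Table 2 intervals would drop them and so narrow a safety rule.

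The cost is one table row, plus the iSRC charter if it repeats the day count. No visits or samples are added. The downside is that a few more Grade 3 values may count toward a hold. If Dose 2 is postponed under Section 5.5 (up to 90 days after Dose 1), the added wording would also take in that later pre-dose sample, so the sponsor should say whether this is intended. If the charter already defines the window by visit, its definition should be carried into Table 10, provided that samples within Days 1 to 29 still count.

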8.2.3.2. Outcome of Safety Evaluation

- If no safety concern is observed, the favorable outcome of safety evaluations will be documented and provided in a written way to the investigators.

- If a safety concern is observed during the safety evaluations or if any of the holding rules is met ([Table 10](#)):
 - The study CSL (or his/her delegate) will be accountable for notifying the investigator to temporarily put all study intervention administration on hold immediately, but all other procedures relating to safety and immunogenicity can continue as planned for participants received at least one dose of study intervention.
 - Following an internal review, GSK will decide to suspend, modify or continue the conduct of the study. This decision will be communicated to the investigator/ IEC/IRB and PMDA as applicable by national regulation.

Refer to Section [10.1.5](#) for details regarding the iSRC and SRT.

